8.3. MISSING DATA

All possible efforts will be made to minimize missing data.

Unless specified otherwise, screening values or pre-dose unscheduled measurements may be used as a baseline value in the event of missing Day 1 pre-dose measurements.

The original data will always be presented in the listings.

8.3.1. Efficacy Data

This is a long-term safety study; since efficacy is a secondary objective and only descriptive presentations of efficacy will be generated there will be no imputation for missing efficacy data. However, all 12MWTs which were stopped prematurely (i.e., before completing 12 minutes) will be reviewed by an adjudication committee to consider whether the reasons are possibly related to the subject’s PMM or study treatment. If deemed at least possibly related, then their data recorded will be used in analyses; if

unrelated the data will be considered missing. The adjudication for the REN001-201 12MWTs will have been conducted as part of the REN001-201 reporting and so these decisions will be used for this study as well. As the descriptive presentation of long-term efficacy data is a secondary objective for this study and treatment is open-label the adjudication of the REN001-202 12MWTs will be performed by Reneo.

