2. INTRODUCTION

[figure not shown]
This Statistical Analysis Plan (SAP) details the statistical analyses for the REN001-202 Open Label study. REN001-202 is an open label long term (48 months) safety study in subjects with Primary Mitochondrial Myopathy (PMM) due to mitochondrial DNA mutations (mtDNA-PMM) or nuclear DNA mutations (nDNA-PMM). Subjects with mtDNA-PMM will have previously completed treatment in Study REN001-201 or participated in Study REN001-101. Subjects with nDNA-PMM who enrol in this study will be mavodelpar (REN001) naïve. As this study is an open label extension study to REN001-201 the two studies will be reported together for the REN001-202 clinical study report (CSR). Therefore, this SAP also details the planned integrated analysis for these two studies from a safety perspective and, the planned analysis will provide long term safety data of up to 54 months exposure to mavodelpar for mtDNA subjects who receive mavodelpar in REN001-201.

Figure 1 below shows the different pathways a subject can enter REN001-202 and the 5 distinct reporting groups. These groups provide the following assessments for mavodelpar 100mg once daily:

- Long-term safety data
- Long-term tolerability
- Bridging data (safety and efficacy) between nDNA-PMM subjects and mtDNA subjects

While efficacy data will be presented, these should be interpreted in a descriptive manner since the design of this open label study, does not enable obtaining either reliable or fully interpretable confirmatory evidence of efficacy, including 'durability of effect'. These limitations regarding long-term efficacy assessments are due to several key issues: the lack of a randomized comparator group, the lack of blinding when assessing effects on effort-dependent outcome measures, and the potential impact of meaningfully informative missing data.

Figure 1 Subject Reporting Groups

The data will be presented in different ways:

- from the start of REN001-202. These data presentations will focus on all 5 reporting groups and only consider data collected in REN001-202. This will allow the assessment of mtDNA-PMM and nDNA-PMM over 48 months of mavodelpar treatment. It will also provide an assessment of:
 - the continued safety of mavodelpar for subjects who received mavodelpar for 6 months in REN001-201;
 - the introduction of mavodelpar for subjects who received placebo for 6 months in REN001-201;

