 - the re-introduction of mavodelpar for subjects who had a break in mavodelpar treatment in studies REN001-101 or REN001-201; and
 - the introduction of mavodelpar for mavodelpar-naïve nDNA subjects.
- from the start of REN001-201. These presentations will focus on reporting Groups 1, 2, 3 and 4a and include data collected in both REN001-201 and REN001-202, except Group 4a, where only REN001-201 data will be included. This will continue to acknowledge the randomization to treatment groups at the start of the REN001-201. It will provide an insight on the influence of a 6-month delay in beginning mavodelpar on subject safety and efficacy outcomes. Importantly, this will summarize the data for all subjects randomized and dosed in REN001-201.
- from the start of REN001 treatment. These presentations will focus on reporting Groups 1, 2, 3 and 4 and include data collected in both REN001-201 and REN001-202 depending on when mavodelpar is initiated. This provides an overall summary of emergent data following the initiation of mavodelpar treatment to mtDNA-PMM

subjects. This is particularly important with respect to safety data (e.g., overall incidence of AEs with mavodelpar treatment).

For further details on the reporting groups refer to [Section 8.2](#).

The purpose of this SAP is to ensure that the data listings, summary tables and figures which will be produced, and the statistical methodologies that will be used, are comprehensive and appropriate for the assessment of study objectives specified in the study protocol. Changes from the analyses specified in the protocol will be identified in the SAP and any amendments to the SAP will be made prior to database lock. The SAP will be the point of reference for the analyses performed for the CSR. Any additional analyses not described in the final SAP or deviations from the final SAP will be documented in the CSR.

The SAP has been developed based on REN001-202 Protocol Version 3.0 and the latest CRF available (Version 6.0, Date 24 April 2023) and REN001-201 Protocol Version 4.0. The subsequent country specific protocol amendments for REN001-202 (see [Appendix 1](#)) do not impact the SAP.

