10. ANALYSIS OF EFFICACY DATA

All analyses will be based on the FAS for the groups from the start of REN001-202 and from the start of REN001-201 unless stated otherwise.

Missing data will be handled using the complete case methodology described in [Section 8.3.1](#).

As the nDNA-PMM subjects will only be recruited from a subset of the REN001-202 sites, summaries may also be presented only including mtDNA-PMM subjects from the same sites. Two separate sets of subjects may be used: the subjects who received mavodelpar in REN001-201 with their data from the start of REN001-201, and the subjects who received placebo in REN001-201 from the start of REN001-202. Consideration will be given to the duration of exposure for nDNA-PMM subjects when summarising the data from the mtDNA-PMM subjects (e.g., if the duration of exposure of nDNA-PMM subjects is up to 6 months, only the first 6 months of data for the mtDNA-PMM subjects will be used).

10.1. 12-MINUTE WALK TEST (12MWT)

Observed, change from baseline and percent change from baseline values will be summarized by visit using descriptive statistics. The associated 95% confidence intervals for the observed, change from baseline and percent change from baseline means will also be presented. The number of subjects withdrawn prior to the visit or with missing data will also be presented. Note missing data will include those subjects who prematurely stop the 12MWT and their reason for stopping is adjudicated as not being possibly related to the subject's PMM or study treatment.

Mean plots for observed, change from baseline and percent change from baseline values, with 95% confidence intervals will be presented by group with visit on the x-axis. A reference line for no change (i.e., $y=0$) will be included in the change from baseline and percent change from baseline plots.

Spaghetti plots for the changes from baseline will be plotted over time. The plots will be split by group. The y-axis will be uniform across the plots to allow comparisons. A reference line for no change (i.e., $y=0$) will be included.

The impact of the subgroups (specified in [Section 8.5](#)) on the 12MWD will also be investigated descriptively. Summaries will be presented by subgroup.

The number of stops and the number of falls will be summarized by visit. If a subject does not walk for the full 12 minutes, then this will be counted as an additional stop when summarizing.

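### SAP 8.3.1 lets the sponsor decide, with no masking or timing rule, which prematurely stopped REN001-202 walk tests are set to missing, and no 12MWD summary shows all recorded distances

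*SAP*

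**What the plan says.** SAP 8.3.1 states that "all 12MWTs which were stopped prematurely (i.e., before completing 12 minutes) will be reviewed by an adjudication committee". The question put to the adjudicators is whether the reason for stopping may be related to the disease or the study treatment. Two outcomes follow: "If deemed at least possibly related, then their data recorded will be used in analyses"; if the reason is judged "unrelated the data will be considered missing". Missing efficacy data are not imputed.

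Decisions on REN001-201 tests are taken over from that study's reporting. For REN001-202, since efficacy is secondary and descriptive and "treatment is open-label the adjudication of the REN001-202 12MWTs will be performed by Reneo", the sponsor decides.

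SAP 10.1 then counts the excluded tests with the other missing values: "Note missing data will include those subjects who prematurely stop the 12MWT and their reason for stopping is adjudicated as not being possibly related". The 12MWD is summarised with 95% confidence intervals and mean plots, both from the start of REN001-202 and from the start of REN001-201. Of the second presentation, split by randomised arm, SAP 2 says: "This will continue to acknowledge the randomization to treatment groups at the start of the REN001-201". It adds that this view gives insight into the effect of a 6-month delay in starting drug.

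**The concern.** Open-label treatment means that current drug is known to everyone. It does not oblige the adjudicator to see how far the subject walked, for how long, at which visit, or which arm the subject had in REN001-201. The SAP gives no rule that withholds any of these, and no rule that decisions are fixed before unblinding or before data are extracted.

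The 12MWD is where this matters. SAP 2 itself lists "the lack of blinding when assessing effects on effort-dependent outcome measures" among the study's limitations, together with informative missing data. The adjudication step adds missing values at the sponsor's discretion to that same outcome. At stake are the early-start versus delayed-start walk-distance curves and the mtDNA versus nDNA descriptions, which SAP 2 presents as bridging data. Neither feeds a hypothesis test.

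**Working it through.** **Who can know what, and when**

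- Protocol 1.4.1 and SAP 3.6: the prior arm is blinded until the REN001-201 database is locked.
- SAP 2 and 13: the interim extract, intended for a regulatory submission, follows that lock, as does the final report.
- SAP 8.3.1: no date is given for adjudication. Decisions taken before the lock would be blind to prior arm; decisions taken after it need not be.
- Access to distance, time walked and visit is not stated. It is possible because nothing excludes it. SAP 4.1 records distance, duration and reason for each incomplete walk.

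**Where the decisions meet**

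SAP 4.1 schedules the 12MWT in REN001-201 at Baseline, Month 3 and Month 6. In REN001-202 it is at Months 3, 6, 12, 18 and 24, which are Months 9, 12, 18, 24 and 30 from the start of REN001-201. In the by-arm series the values up to Month 6 carry the REN001-201 decisions and the later ones carry the sponsor's decisions. The change of process coincides with the switch of placebo subjects to drug.

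**What a reader can see**

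SAP 8.3 and 10.1 keep original values in the listings. The 12MWT listing flags early stops judged possibly related to PMM. It is not specified to flag those judged unrelated. In the tables, excluded tests are merged into the missing count, and no summary or plot uses all recorded distances.

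**Size**

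The plan states no figure to reproduce. It gives neither an early-stop rate nor the distances of early-stopped tests, so the inputs below are assumptions.

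Let s be the share of tests at a visit adjudicated unrelated (not the share that stops early), and let these lie d metres below the mean of the rest. With all tests kept, the mean is (mean of the rest) − s × d. Excluding them raises the observed mean by s × d.

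| s | d = 200 m | d = 300 m | d = 400 m |
|---|---|---|---|
| 2% | 4 m | 6 m | 8 m |
| 5% | 10 m | 15 m | 20 m |
| 10% | 20 m | 30 m | 40 m |

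- Between arms, equal s and d cancel. With s = 5% in one arm and 2% in the other at d = 300 m, the difference moves by 15 − 6 = 9 m.
- In a small cell, one excluded test among N moves the mean by d / N. SAP 8.5 allows 12MWD subgroups of 5 subjects, so at d = 300 m this is 300 / 5 = 60 m.
- The bias from unmasked adjudication is smaller than s × d. If unmasked staff exclude 5% and masked staff would have excluded 2 of those 5 points, the excess is d × (0.05 − 0.02) / (1 − 0.02) = 300 × 0.03 / 0.98 = 9.2 m, against 15 m for the whole exclusion.
- Change from baseline can move the other way. Subjects enrolling under Options 2 to 4 have their baseline walk in REN001-202 (Protocol 6.1.2 to 6.1.4). If a share s has a baseline short by d and a normal later walk, their change is d too large. Excluding that baseline lowers the mean change by s × d when no other baseline is used. SAP 8.3 and 8.6 may instead substitute an earlier value.

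**The case against.** The SAP discloses the choice and gives its reasons. It says efficacy is to be read descriptively, plans no test (SAP 8.1), and has safety as its primary endpoints. The threshold for keeping a test is low, so in a population enrolled for exercise intolerance or muscle pain many early stops may be kept. Excluding a stop that is truly unrelated is sensible. Open-label effort is probably a larger source of bias than adjudication, and masking does not touch it. Medical text may reveal timing or genotype even to a masked adjudicator. Protocol 8.1.3 also requires data-issue decisions to be documented before database lock.

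Most of this stands, and it limits the point to a cheap improvement. The Protocol 8.1.3 review does not name adjudication, does not mask it, and does not cover the interim extract. Being descriptive is also a reason to show all recorded distances, since the tables and plots are the whole product.

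A reader might infer four stronger things that the documents do not support:

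- **Data are erased and the effect is untraceable.** Listings keep the original values, and excluded tests appear, though merged, in the missing count.
- **Every early stop is removed.** Only those judged unrelated are.
- **Exclusion always favours the drug.** An early-stopped test need not be below average, and an excluded short baseline can lower the mean change.
- **A masked, independent process was replaced by an unmasked one.** The documents do not say whether the REN001-201 adjudication was masked or who sat on it.

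**Conclusion.** The point holds as a weakness of method on a descriptive outcome, secondary for mtDNA and exploratory for nDNA subjects. The sponsor decides which early-stopped REN001-202 walks count, no rule masks it or fixes when it decides, and the prior arm can be known after the REN001-201 lock. The observed visit mean shifts by s × d, which is 4 to 40 m over the assumed ranges s = 2% to 10% and d = 200 to 400 m. The bias is only the part that masked adjudication would have decided otherwise. Its size, and its direction for change from baseline, cannot be determined from the documents. Nothing here shows that the sponsor will use the information improperly, and no safety conclusion depends on it.

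**What to change.** In SAP 8.3.1, replace the sentence assigning REN001-202 adjudication with text to this effect:

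> Prematurely stopped REN001-202 12MWTs will be adjudicated by sponsor staff using only the recorded reason for stopping and relevant adverse event or medical text. As far as feasible they will be masked to distance, time walked, visit, REN001-201 arm and reporting group. Decisions will be fixed and documented before each data extraction.

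In SAP 10.1, add one supportive 12MWD summary that uses every recorded distance whatever the adjudication. Show the number of tests adjudicated unrelated by group and visit, separately from other missing data.

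The cost is SAP wording, a masked line listing for the same staff, one repeated table and one extra row of counts. No new adjudicators, data or site work are needed. The drawbacks are that adjudicators see less context for each case and that masking may be imperfect. The supportive summary should be read beside the main one, not in place of it, because it restores stops that were truly unrelated.

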8.3.2. Pharmacokinetic Data

Missing data will not be imputed.

Mavodelpar concentrations reported as below the limit of quantification (BLQ) will be taken as zero for linear plots, and equal to the LLOQ for log-linear plots. BLQ will be taken as zero for the computation of descriptive statistics except for the geometric mean and geometric CV%, where they will be set to the LLOQ.

8.3.3. Safety Data

AEs with missing classification will be queried prior to database lock. However, if there are missing classifications in the final data the following will be assumed:

- missing causality will be taken as treatment related
- missing severity will be taken as severe

Missing seriousness will not be imputed. Such cases will be discussed in the CSR.

Handling of missing dates/times for the start/stop of medications and adverse events are detailed in [Sections 9.4](#) and [12.1](#) respectively.

Laboratory values that are less than the LLOQ or greater than the upper limit of quantification (ULOQ) will be set to the LLOQ or ULOQ respectively, for the calculation of descriptive statistics.

There will be no imputation for missing DXA data.

8.4. VISIT WINDOWS

Data will be assigned to ‘analysis’ visits using windowing (see table below). If more than one assessment (including the early termination or unscheduled assessments) falls within the same defined window, the on-treatment assessment closest to the target day with non-missing data will be used for analysis. If the scheduled visit assessment is on-treatment and within the analysis window, then this will be used irrespective of other unscheduled assessments within the analysis window. If two assessment dates are at the same distance from the target day, the latest on-treatment assessment with non-missing data will be used for analysis. Off-treatment assessments will only be assigned to a visit window in the absence of an on-treatment assessment within the analysis window.

This is the same approach as used in the REN001-201 SAP and therefore the REN001-201 data will have the same analysis visit windowing assigned as per the REN001-201 CSR.

To assess whether a REN001-202 visit is within the analysis window the day relative to the start of REN001-202 will be used. This will mean that for subjects who enrol at REN001-201 FU the interruption in study drug during the REN001-201 FU period will be ignored.

Study	Original Visit	Visit Name for Combined Study Summaries	Target Day ¹	Protocol Visit Window	Analysis Window ¹	Analysis Interval
REN001-201	Baseline	Baseline	1	NA	≤1*	NA
	Week 2	Month 0.5	14	±3	8 – 20	13 (±6)
	Week 4	Month 1	28	±3	21 – 35	15 (±7)
	Week 12	Month 3	84	±7	63 – 105	43 (±21)
	Week 18	Month 4.5	126	±7	106 – 146	41 (±20)
	Week 24	Month 6	168	±7	147 – 189	43 (±21)
REN001-202	Baseline	Month 6	1	NA	≤1*	NA
	Month 1	Month 7	28	±3	21 – 35	15 (±7)
	Month 3	Month 9	84	±7	63 – 105	43 (±21)
	Month 6	Month 12	168	±7	147 – 189	43 (±21)
	Month 9 [^]	Month 15 [^]	252	±21	211 – 293	83 (±41)
	Month 12	Month 18	336	±21	294 – 378	85 (±42)
	Month 15 [^]	Month 21 [^]	420	±21	379 – 461	83 (±41)
	Month 18	Month 24	504	±21	462 – 546	85 (±42)
	Month 24	Month 30	672	±21	630 – 714	85 (±42)
	Month 30	Month 36	840	±21	798 – 882	85 (±42)
	Month 36	Month 42	1008	±21	966 – 1050	85 (±42)
	Month 42	Month 48	1176	±21	1134 – 1218	85 (±42)
	Month 48	Month 54	1344	±21	1302 – 1386	85 (±42)

NA=not applicable.

¹ Target day and analysis windows are relative to start of each study.

* Baseline values must be prior to dosing if time of assessment is recorded.

[^] Month 9 and Month 15 (original) visits are only applicable for German sites.

Subjects can have more than one baseline defined depending on which reporting group is used. [Section 8.6](#) provides more details on the baseline definitions.

REN001-202 follow-up visit, by design, is after the last dose of study drug and should not be allocated to on-treatment visits. Similarly, REN001-201 follow-up visit should not be assigned to an on-treatment visit in REN001-202.

Windowing will not be used for the DXA scan data. Subjects can have a maximum of 4 DXA scans across the studies and these will be assigned to the nominal scheduled visits.

If an unscheduled or early termination visit is mapped to a scheduled visit, then the type of visit will be identified in the appropriate listing together with the visit that it has been mapped to. In addition, data collected outside these windows will not be attributed to an analysis window and will only be listed, unless specified otherwise in [Section 10](#) and [Section 10](#). Any scheduled visit outside the window will be identified on the appropriate listing.

8.5. SUBGROUPS

Subgroups will only be assessed for the purposes of exploring the consistency of effects. Subgroup analyses are planned for adverse events, 12-minute Walk Distance (12MWD) and DXA endpoints. For these analyses only subgroup categories with 5 or more subjects will be summarized. The subgroups that will be used for each endpoint are defined in the table below, the remaining subgroups will only be used in the summary of baseline characteristics.

Endpoint	Subgroups
Adverse events	Age, sex, race (excluding Other race category)
12MWD	Mutational genotype (both subgroups defined below), baseline 12MWD
DXA	Menopausal status

The subgroups are defined as:

- Age: <65 years or ≥65 years
- Sex: male or female
- Race: black/African American, Asian, American Indian/Alaska Native, Native Hawaiian/Pacific Islander, white or other
- Mutational genotype: there will be 2 subgroups, one which identifies the stratification groups (i.e., m.3243A>G or Other) and a second which further splits out the 'other' category genotype (i.e., m.3243A>G, m.8344A>G, mt deletion or Other). To split out the 'other' genotype category into these extended levels, first the m.8344A>G subjects will be identified from the other description free text

field; then mt deletion subjects will be identified as subjects with a single large deletion gene defect; all remaining subjects will be categorized as Other.

- Syndromatic phenotype: as identified from the additional symptoms of PMM eCRF page.
 - chronic progressive external ophthalmoplegia (CPEO)
 - Kearns-Sayre syndrome (KSS)
 - Leigh and Leigh-like syndrome
 - maternally inherited deafness and diabetes (MIDD)
 - maternally inherited Leigh syndrome (MILS)
 - mitochondrial encephalomyopathy with lactic acidosis and stroke-like episodes (MELAS)
 - mitochondrial neurogastrointestinal encephalopathy (MNGIE)
 - myoclonic epilepsy with ragged red fibers (MERF)
 - neuropathy; ataxia; and retinitis pigmentosa (NARP)
 - Pearson syndrome (sideroblastic anemia and pancreatic dysfunction)
 - other
- Baseline 12MWD: there will be 2 subgroups ≤ 500 m or > 500 m and ≤ 650 m or > 650 m
- Country: all countries that randomized a subject
- Region: North America (USA and Canada), Europe or Australia/New Zealand
- Clinically significant vitamin D deficiency at baseline, defined as < 30 nmol/L: yes, no
- Baseline PROMIS T-score: ≤ 60 or > 60
- Menopausal status: males, pre-menopausal females or post-menopausal females. Post-menopausal females have a screening FSH value ≥ 23.0 IU/L and with either a date of last menstrual period > 1 year ago from date of first dose or a confirmed clinical history of sterility. Female subjects whose last menstrual period was > 1 year ago but do not have a screening FSH value will also be assumed to be post-menopausal. Female subjects who have a clinical history of sterility but do not have a screening FSH value cannot be classified. This subgroup will only be used for DXA and laboratory bone marker analyses.

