4. EFFICACY ASSESSMENTS

The sections below detail the efficacy assessments, including any derivations required for the efficacy secondary endpoints. The descriptive presentations of data regarding these endpoints are detailed in [Section 10](#).

Details concerning the baseline used in the derivation of changes from baseline are provided in [Section 8.6](#).

4.1. 12-MINUTE WALK TEST (12MWT)

In REN001-201 subjects will perform the 12MWT at Screening, Baseline, Week 12 (Month 3) and Week 24 (Month 6). In REN001-202 subjects will be assessed at Baseline, Months 3, 6, 12, 18 and 24; which from the start of REN001-201 are equivalent to Months 6, 9, 12, 18, 24 and 30. It will also be assessed at an early termination visit if the subject withdraws from the study. In addition, nDNA-PMM subjects will have a screening 12MWT assessment.

The test measures the distance a subject can walk on a flat, hard surface in a period of 12 minutes. To reduce site variability sites will be fully trained to administer the test according to the REN001-202 exercise manual. If the subject does not walk for the full 12 minutes, the distance walked and the duration of time walked will be recorded, along with the reason for stopping prematurely.

Handling of missing or incomplete 12MWT are detailed in [Section 8.3.1](#).

For each visit changes from baseline and percent changes from baseline will be calculated.

Additionally, the exploratory endpoints, distance walked in the first 6 minutes (from start of test up to 6 minutes) and the last 6 minutes (>6 minutes up to 12 minutes) will be derived. As only the number of completed laps are recorded each minute with the final minute recording any partial lap ongoing at the end of the 12 minutes, the distance walked in the first 6 minutes will be the total number of completed laps multiplied by the lap distance (20 meters). The distance walked in the last 6 minutes will then be the total distance walked minus the distance walked in the first 6 minutes. Note, in most cases, this will be an underestimate of the distance walked in the first 6 minutes and an over-estimate of the distance walked in the last 6 minutes.

Pre and post exercise measurements for heart rate and blood pressures are collected. The changes (post – pre) will be calculated.

4.2. PATIENT-REPORTED OUTCOMES MEASUREMENT INFORMATION SYSTEM (PROMIS) SHORT FORM – FUNCTIONAL ASSESSMENT OF CHRONIC ILLNESS THERAPY (FACIT) FATIGUE 13A

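### The 12MWD subgroup tables sort subjects by the same single baseline walk that is subtracted to give change, so regression to the mean adds a spurious low-versus-high gap on top of any true change

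*SAP*

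**What the plan says.** SAP 8.5 lists the 12MWD subgroup factors as "Mutational genotype (both subgroups defined below), baseline 12MWD" and defines the second as follows: "Baseline 12MWD: there will be 2 subgroups", one split at 500 m and one at 650 m. It gives the purpose: "Subgroups will only be assessed for the purposes of exploring the consistency of effects".

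SAP 10.1 specifies for 12MWD: "Observed, change from baseline and percent change from baseline values will be summarized by visit using descriptive statistics", with 95% confidence intervals for the means. It adds that the impact of the subgroups "on the 12MWD will also be investigated descriptively" and that "Summaries will be presented by subgroup".

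SAP 8.2 defines change as the visit value minus the baseline value. SAP 8.6 gives each presentation one baseline, the last non-missing assessment before dosing in the relevant study. SAP 8.5 does not say which of a subject's two possible baselines sets the class. SAP 8.6 and 9.2 point to the one belonging to the presentation. No averaging of pre-dose walks, baseline adjustment or separate classifying walk is specified.

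Earlier walks exist. SAP 4.1 schedules REN001-201 walks at screening, baseline, Week 12 and Week 24, and a screening walk for nDNA-PMM subjects. SAP Appendix 2 puts the REN001-201 screening walk at least 4 weeks before baseline.

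**The concern.** A single walk is a subject's usual distance plus that day's error. Subjects at or below the cut include some who walked unusually badly that day, and those above it include some who walked unusually well. The same error enters the change with a minus sign, so the low class tends to rise and the high class to fall even if nobody's usual distance changes.

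The table is meant to show whether the effect is consistent across walking ability, and this mechanism distorts exactly that comparison. A reader could take the gap as evidence that weaker walkers gain more from REN001. In the start-of-REN001-202 presentation there is no untreated column against which to set it.

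**Working it through.** **Inputs from the documents.** Cut-offs of 500 m and 650 m (SAP 8.5); change as a simple difference (SAP 8.2); one pre-dose value per presentation (SAP 8.6); about 150 mtDNA-PMM subjects (SAP 3.5). The plan gives no figure for 12MWD variability, so there is none to reproduce.

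**Assumed inputs.** Normal distances, mean 650 m, observed SD 200 m, within-person SD w of 40, 60 or 80 m, and no true change.

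**Formula.** With test-retest correlation r, 1 − r = w²/SD². The expected change in a class is −(1 − r) × (class mean of baseline − overall mean).

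**Class means.**
- 500 m cut: z = (500 − 650)/200 = −0.75, φ(z) = 0.3011, Φ(z) = 0.2266. The low class lies 200 × 0.3011/0.2266 = 265.8 m below the mean. The high class lies 200 × 0.3011/0.7734 = 77.9 m above it. They are 343.6 m apart.
- 650 m cut: z = 0, and each class lies 200 × 0.3989/0.5 = 159.6 m from the mean.

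| w (m) | 1 − r | 500 m cut: low / high / gap (m) | 650 m cut: low / high / gap (m) |
|---|---|---|---|
| 40 | 0.04 | +10.6 / −3.1 / 13.7 | +6.4 / −6.4 / 12.8 |
| 60 | 0.09 | +23.9 / −7.0 / 30.9 | +14.4 / −14.4 / 28.7 |
| 80 | 0.16 | +42.5 / −12.5 / 55.0 | +25.5 / −25.5 / 51.1 |

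Means of 600 to 700 m give gaps of about 13 to 58 m. Over a wider range (mean 550 to 750 m, SD 150 to 250 m, r from 0.80 to 0.95) the low class shows +3 to +76 m and the high class −1 to −53 m. The sign is the same throughout.

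**Effect on the planned intervals.** In simulated trials with no true change, 150 subjects in one column (mean 650 m, SD 200 m) were split at 650 m. The 95% interval for mean change excluded zero in the artefact's direction in about 19 to 20% of trials per class at r = 0.95, 34% at r = 0.90 and 61% at r = 0.80. The nominal rate is 2.5%. Smaller columns would show this less often.

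**Randomised arms.** When both arms are classified by the same pre-randomisation baseline, the simulated between-arm difference within a class was about 0 m. In the start-of-REN001-201 tables that baseline and class stay fixed at every later visit.

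**Classifying by an earlier walk.** If the errors of the walks are independent and correlation does not fall with time, the simulated change was within 0.2 m of zero in both classes. Averaging the screening and baseline walks only halves the artefact (at r = 0.90 and the 650 m cut, +8.1/−8.1 m instead of +16.0/−15.9 m).

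If correlation falls with time, a residual gap remains at the 500 m cut:

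residual = (correlation of earlier walk with baseline − correlation of earlier walk with follow-up) × 343.6 m.

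- A fall from 0.91 to 0.85 leaves 0.06 × 343.6 = 21 m.
- A harsher assumption is correlation 0.91 × 0.95 per 6 months apart, with the earlier walk 6 months before baseline and follow-up at Month 24. The residual is (0.91 × 0.95 − 0.91 × 0.95⁵) × 343.6 = (0.8645 − 0.7041) × 343.6 = 55 m. The gap by baseline class is then (1 − 0.91 × 0.95⁴) × 343.6 = 0.2588 × 343.6 = 89 m.

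The earlier-walk table is better, but not guaranteed to be free of the artefact.

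**The case against.** **Descriptive purpose.** No testing is planned, no decision rule uses this table, and the SAP Introduction already limits what the efficacy data can show, citing the lack of a randomised comparator, the lack of blinding and informative missing data. This stands and lowers the consequence. It does not dispose of the point, because none of those caveats tells a reader to expect weak and strong walkers to diverge without any drug effect.

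**Size.** The metres are assumed, and the range is about fourfold. This stands. Only the direction is firm.

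**Legitimate question.** Summarising outcome by status at entry is a reasonable description. This stands, and is a reason to keep the planned table.

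**Replacing the class would do harm.** REN001-101 subjects have no earlier walk in these data. SAP 3.8 treats the two participations of REN001-201 Exit subjects as separate subjects. SAP 9.2 uses the same subgroup in the baseline characteristics. In the REN001-202 tables, some subjects would be classed by a walk taken before 24 weeks of mavodelpar and nDNA-PMM subjects by an untreated walk some weeks before baseline. These objections stand against replacement, but not against an added table.

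**Stronger readings.** A reader might infer that any low-versus-high difference is purely artefact, or that strong walkers must show a net decline. The documents support neither: real change, real heterogeneity and disease progression can all add to the artefact. A reader might also infer that the REN001-201 placebo arm protects only up to Month 6. What ends then is the untreated comparison. Both arms keep the same baseline and class, so the early-versus-delayed contrast within a class remains protected apart from differential dropout.

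**Conclusion.** The point holds as a bias that contributes to the subgroup tables, not as a claim that they show nothing else. On the natural reading of SAP 8.5, 8.6 and 10.1, the low class is pushed up and the high class down whenever the walk is less than perfectly repeatable. The false gap is about 13 to 55 m if the mean is 650 m, the SD 200 m and the within-person SD 40 to 80 m, none of which the documents give.

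The exposure lies mainly in the start-of-REN001-202 tables. In the start-of-REN001-201 tables the low-versus-high gap within an arm is affected, but the between-arm contrast within a class is not, apart from differential dropout. If the sponsor intends the REN001-201 class to be carried into the REN001-202 tables, the problem there is smaller, but SAP 8.5 would have to say so. The change is worth making because it is cheap. It is not critical, because no formal conclusion rests on the table.

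**What to change.** In SAP 8.5 and 10.1:

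1. Keep the planned baseline-12MWD subgroup table and its use in the SAP 9.2 baseline characteristics. State which baseline defines the class in each presentation.
2. Repeat the 12MWD change and percent-change summaries with the same 500 m and 650 m cut-offs, classifying by a walk earlier than the one used as baseline:
   - start of REN001-201: the REN001-201 screening walk;
   - start of REN001-202: one named earlier REN001-201 walk for Week 24 and follow-up enrollers, and the screening walk for nDNA-PMM subjects.
3. In the start-of-REN001-202 repeat table, leave REN001-101 and REN001-201 Exit subjects unclassified. In either repeat table, do the same for anyone whose classifying screening walk served as baseline under SAP 8.3. Show their number.
4. State that consistency of effect across baseline 12MWD is judged from the repeat table and the randomised between-arm contrast, not from the low-versus-high gap in the baseline-class table. Add that a smaller residual gap can remain if correlation falls with time, and that the classifying walk differs in timing and treatment history between mtDNA-PMM and nDNA-PMM columns.

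Cost: one extra table set, a few sentences in the SAP and some unclassified subjects. No new data are needed.
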